12 STATISTICAL CONSIDERATIONS

12.1 Study Endpoints

Primary safety endpoints are the incidence of hypotension. Secondary endpoints include PK and preliminary effectiveness (PK/PD).

12.2 Sample Size Considerations

The sample size of 30 (sildenafil) in each dose group is sufficient to estimate hypotension incidence with sufficient precision. Table 8 provides widths for 95% Wilson confidence intervals in the dose groups of size 30 and the total sildenafil treatment cohort of 90 with different incidence rates. If hypotension occurs with an incidence rate of 0.05, it has a 78% chance of being observed at least once in a dose group and a 99% chance of being observed at least once in the total sildenafil cohort.

Table 8 Widths for 95% Wilson Confidence Intervals

N = 30			N = 90		
Rate	Width	95% CI	Rate	Width	95% CI
0.1	0.22	0.04-0.26	0.1	0.13	0.05-0.18
0.2	0.28	0.10-0.37	0.2	0.16	0.13-0.29
0.3	0.31	0.17-0.48	0.3	0.19	0.22-0.40

Abbreviations: CI, confidence interval; N, number of participants

Populations for Analysis

Intention to Treat (ITT) Population: Participants whose parent or guardian signs informed consent and are randomized.

Per Protocol (PP) Population: Participants who receive at least 7 days of study medication within 9 days (to allow for one pause in medication administration for up to 48 hours).

Safety Population: Participants who receive at least 1 dose of study medication.

PK Population: All participants who have at least one interpretable PK sample.

12.3 Planned Interim Analyses

12.3.1 Safety Review

The DSMB will complete an unblinded review of the safety data after 80% of infants within the cohort complete 14 days of treatment. Enrollment to the next cohort will not begin until after the DSMB has completed their review and provided a recommendation that the study proceed.

See Section 9.6 for additional details for halting rules due to safety concerns.

12.4 Final Analysis Plan

General Analysis Conventions

A comprehensive overview of planned statistical analyses will be provided in a separated statistical analysis plan.

Analysis results will be presented by placebo versus sildenafil, overall and by dose cohort. Data from participants assigned to placebo across cohorts will be pooled in result presentations.

Descriptive statistics such as number of observations, mean, median, standard deviation, minimum and maximum will be presented by treatment groups for continuous variables (such as age, weight, etc.). Other descriptive statistics such as counts, proportions, and/or percentages will be presented by group to summarize discrete variables (such as race, sex, etc.).

Participant Disposition and Study Drug Exposure

Study disposition, demographic and baseline characteristics, and study medication exposure will be summarized for the ITT Population. Study drug administration will be summarized by route (IV vs enteral), number of days of dosing, and reasons for final discontinuation of study drug.

Demographic and baseline characteristics

Demographic and baseline characteristics will include race, age, sex, and selected clinical variables recorded prior to initiation of study drug.

Safety

The primary safety endpoint is number and percent of hypotension events and will be summarized for the PP and Safety Population.

Serious adverse events will be presented overall and by each Medical Dictionary for Regulatory Activities (MedDRA) system organ class and preferred term. Severity and relationship to sildenafil or placebo will be provided.

Events of special interest will be presented overall and summarized by participant characteristics.

Prior and concomitant medications will be summarized by World Health Organization (WHO) drug class.

Laboratory data, including change from baseline, will be tabulated by treatment groups.

PK Analysis Plan

A comprehensive overview of planned PK analyses will be provided in a separated PK analysis plan.

Pharmacokinetic parameters will be estimated by population PK approach using nonlinear mixed effects modeling in NONMEM. The influence of covariates on PK parameters will be explored.

Biomarkers

We will relate the concentration of biomarkers (Section 8.2) to the development of and severity of PH in participants exposed to placebo.

Preliminary Effectiveness

A multivariable mixed-effects model will be used to explore the relationship between the maximum and total dose of sildenafil and change in PH, death, and death or PH at 28 days of study drug and at the end of hospitalization or 52 weeks PMA, whichever comes first. We will use 52 weeks PMA because we found that 95% of infants with severe BPD died or were discharged home by this time.⁷

Planned sensitivity analyses of the primary endpoint

To address the potential effect of multiples enrolled in the study on the primary endpoint, we will conduct the following 2 sensitivity analyses:

- Sensitivity analysis #1 using only the first randomized sibling from any multiple gestations.
- Sensitivity analysis #2 using generalized estimating equations (GEE) with log link random effect for siblings to compute ratios of hypotension between the sildenafil and placebo groups.

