Neonatologists frequently use sildenafil to treat infants with pulmonary hypertension. Two case reports documented the successful resolution of PH, measured by echocardiogram, in premature infants treated with sildenafil.^{27,28} In a small case series, enteral sildenafil at a dose range of 1.5-8 mg/kg/day in 25 premature infants with a median gestational age of 28 weeks (range 23-41 weeks) with lung disease (72% with BPD) resulted in improved hemodynamics by echocardiogram.²⁹ A retrospective case series of 23 preterm infants with median gestational age of 26 weeks treated with 1-7.3 mg/kg/day of oral sildenafil found a substantial improvement in BPD related PH based on echocardiography in 71% of patients for whom echocardiographic data were complete (15/21).³⁰ These data confirm that neonatologists usually treat PH in infants with BPD and are likely unwilling to randomize to placebo; thus, a prevention approach is needed.

Neonatologists are using sildenafil without safety data. Neonatologists are increasingly using sildenafil in premature infants despite a lack of sufficient safety data, including data related to hypotension and retinopathy of prematurity (ROP). Despite neonatal medicine's long history of catastrophic adverse events (AEs) resulting from inadequate study of drugs prior to their widespread use,³¹⁻³⁴ the majority of drugs used in premature infants, including sildenafil, have undergone insufficient study to receive FDA labeling for this population.³⁵⁻³⁹ Extrapolating drug safety and dosing from adults underestimates the complicated physiology of premature infants, who have (1) larger extracellular fluid volume per unit body weight, (2) immature renal and hepatic function, and (3) disease-related changes in metabolizing organ function, each of which can alter drug disposition.^{40,41} Improper use of drugs in these vulnerable patients leads to increased treatment failure, AEs, mortality, and long-term morbidities.⁴² Sildenafil studies specifically designed for premature infants with BPD are urgently needed. These studies should initially focus on characterizing PK and safety in infants to inform the design of a pivotal efficacy trial.

Sildenafil is increasingly used off-label in premature infants with BPD: A review of data from the Mednax Clinical Data Warehouse, a real-world data source representing approximately 20% of US Neonatal Intensive Care Unit (NICU) admissions,⁴³ found an

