3.2.2.2 Preliminary Effectiveness

The presence or absence of PH will be determined using central review by blinded pediatric cardiologists of echocardiograms performed at the end of the study period.

The developed population PK model will be linked to the diagnosis of PH made by echocardiography at the end of the study period to develop a population PK/PD model. We will use the model to simulate the effect of variable sildenafil exposures on the probability of developing PH.

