6 STUDY INTERVENTION

6.1 Study Product Description

In the US, sildenafil, in both IV and for oral suspension, has been approved for use in other populations and for other indications by the FDA¹.

Study dosing and escalation are described in Table 3. Refer to Section 6.1.3 for study drug packaging and labeling.

Table 3 Number of Participants (N) and Dosing Scheme

Cohort ¹	Treatment Group		Sildenafil Dosing ² (mg/kg q 8 hours)		Total (N)
	Placebo (N)	Sildenafil (N)	IV	Enteral	
1	10	30	0.5	1	40
2	10	30	1	2	40
3	10	30	2	4	40

Abbreviations: IV, intravenous; N, number of participants; q, every

1 Participants will be enrolled into cohorts sequentially (i.e., Cohort 1 then Cohort 2 then Cohort 3) based on safety.

2 Route of administration, IV or enteral, is left to investigator discretion.

Dose escalations for each sequential cohort will proceed as summarized in Table 4. DSMB safety review (Section 10) will be required prior to enrolling the next cohort.

Table 4 Dose Escalations for Each Sequential Cohort

	Study Days (Dose Numbers)							
	1-2 (1-6)	3-4 (7-12)	5-6 (13-18)	7-8 (19-24)	9-10 (25-30)	11-12 (31-36)	13-14 (37-42)	15 + (43 +)
Sildenafil Dose (mg/kg)								
Cohort 1								
IV	0.25	0.5	0.5	0.5	0.5	0.5	0.5	0.5
Enteral	0.5	1	1	1	1	1	1	1
Cohort 2								
IV	0.25	0.5	0.75	1	1	1	1	1
Enteral	0.5	1	1.5	2	2	2	2	2
Cohort 3								
IV	0.25	0.5	0.75	1	1.5	1.75	2	2
Enteral	0.5	1	1.5	2	3	3.5	4	4

Abbreviation: IV, intravenous

Dose escalation will occur if the infant is:

1. Receiving exogenous oxygen or respiratory support (nasal cannula or positive pressure from any device); and
2. AST < 225 U/L and ALT < 150 U/L at last check (within 14 days) prior and closest to dose increase.

An infant will meet respiratory criteria for dose escalation only if the infant is receiving exogenous oxygen or respiratory support (nasal cannula or positive pressure from any device) for at least 12 hours before the dose escalation. Infants who do not initially qualify for escalation should be reevaluated daily to ascertain whether they meet these criteria, and escalation must occur within 24 hours of an infant meeting all dose escalation criteria (respiratory and laboratory). If escalation does not occur within this timeframe, then a protocol deviation must be recorded.

Adjusting dose for weight

The actual weight should be reviewed weekly (plus or minus one day, Section 4.2) and the dose of the study drug may be adjusted.

Weaning Period Schedule

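### Section 12.4 analyses preliminary effectiveness only by dose received, which death and illness can shorten, and specifies no randomised sildenafil-versus-placebo effectiveness estimate

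*Combined protocol and SAP*

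**What the plan says.** Sections 3.1.2, 3.2.2.2 and 12.1 make preliminary effectiveness secondary, separate from the tertiary outcomes in Section 3.3. Section 3.2.2.2 names the outcome: "The presence or absence of PH will be determined using central review by blinded pediatric cardiologists" from echocardiograms at the end of the study period. It then links that outcome to a population PK model.

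Under Preliminary Effectiveness, Section 12.4 gives one analysis, a multivariable mixed-effects model to "explore the relationship between the maximum and total dose of sildenafil and change in PH, death, and death or PH at 28 days". The first time is counted in days on study drug; the second is "at the end of hospitalization or 52 weeks PMA, whichever comes first". No dose metric, outcome or time leads. The analysis population, the covariates and the handling of placebo infants are not stated.

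The general conventions in Section 12.4 add: "Analysis results will be presented by placebo versus sildenafil, overall and by dose cohort", with placebo pooled over cohorts. The only between-arm ratio described is for hypotension, in the sibling sensitivity analysis. Detail is deferred to a separate SAP, which is not in the supplied text.

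Three rules tie dose received to the infant's course:
- Section 6.1: "An infant will meet respiratory criteria for dose escalation only if the infant is receiving exogenous oxygen or respiratory support" (for at least 12 hours), and only with liver enzymes below set limits.
- Section 5.5.1: study drug is withdrawn if, among other triggers, a vasopressor or inhaled nitric oxide is started.
- Death ends dosing.

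**The concern.** Section 5.4.1 randomises infants 3:1 within cohort, so a sildenafil-versus-placebo comparison is protected from confounding. The dose an infant went on to receive is not. An infant who dies in week 2 has a low total dose because of the death. An infant who deteriorates and starts inhaled nitric oxide has dosing stopped. In both cases low dose goes with a bad outcome whatever the drug does, so more drug appears to protect. The escalation rule works the other way on maximum dose: infants who come off all support stop escalating, so higher maximum dose marks persistent lung disease and leans toward apparent harm.

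Section 2.2 says that studies of this kind should "inform the design of a pivotal efficacy trial". A dose-outcome association produced by truncated dosing could be carried into that design as evidence of benefit.

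**Working it through.** **1. The plan's own figures.** Section 12.2 gives figures for hypotension only. At incidence 0.05, 1 − 0.95^30 = 0.785 and 1 − 0.95^90 = 0.990, matching the stated 78% and 99%. The Table 8 Wilson intervals also reproduce within 0.01. There is no effectiveness figure to reproduce.

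**2. Number of dose-outcome pairs.** 2 dose metrics × 3 outcomes × 2 times = 12. If the two times attach only to death or PH, the count is 2 × (1 + 1 + 2) = 8.

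**3. How death sets total dose.** From Table 4 (IV, three doses a day), cumulative mg/kg:

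| Cohort | 28 days | 14 days |
|---|---|---|
| 1 | 6×0.25 + 78×0.5 = 40.5 | 6×0.25 + 36×0.5 = 19.5 |
| 2 | 6×(0.25+0.5+0.75) + 66×1 = 75.0 | 9 + 24×1 = 33.0 |
| 3 | 6×(0.25+0.5+0.75+1+1.5+1.75) + 48×2 = 130.5 | 34.5 + 6×2 = 46.5 |

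An infant who dies after 14 days has 36% to 48% of the full total for the cohort (46.5/130.5 to 19.5/40.5), with no drug effect involved.

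**4. Size of that bias with an inert drug.** Simulated trials of 90 sildenafil and 30 placebo infants on the Table 4 IV ladder. Assumptions not in the documents: 5% dead by Day 28, two-sided 0.05, and a score test in place of the unspecified mixed model. Chance that total dose against death at 28 days is nominally significant:
- sildenafil infants only: 66%
- all 120 infants, placebo as dose 0: 34%
- sildenafil infants, stratified by cohort: 99%
- randomised contrast for the same outcome: about 3%

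Removing any link between severity and outcome gives 68%, 36% and 99%, so truncation alone is enough. A separate check (3,000 trials, day of death uniform over Days 1–28, no severity link) gave 69%, 36% and 99%, against 4% for the randomised contrast. Every significant sildenafil-only result was in the protective direction. With 2% dead the three figures were 36%, 9% and 83%; with 10% dead they were 92%, 70% and 100%.

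**5. Illness-driven stopping.** With 20% stopping early, linked to severity, and no truncation by death, at least one of the 12 pairs is nominally significant in 32% (sildenafil only), 25% (placebo as 0) or 50% (stratified). Without gate, stopping or death truncation, the two unstratified analyses give 17% to 18%.

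**6. The escalation gate.** Assume 10%, 20% or 30% of infants off all support in the first 12 days, with severity acting on both recovery and outcome (log odds ratio 1 per SD). The any-of-12 rate is 0.209 with no gate and 0.208, 0.241 and 0.265 with it. The null odds ratio for death or PH per 2 mg/kg of maximum dose is 1.11, 1.21 and 1.32.

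**7. The randomised contrast.** Across all the scenarios in the main simulation its false-positive rate is 2.8% to 6.0%. Its 95% half-width is 1.96 × √[p(1−p)(1/30 + 1/90)]: 0.165 at p = 0.20 and 0.179 at p = 0.25. Power for 20% versus 10% is about 32%.

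**The case against.** Several points on the other side stand.

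- A reader might infer that no effectiveness outcome is named. That is wrong: Section 3.2.2.2 names centrally read PH, and Section 12.1 ties the endpoint to PK/PD.
- A reader might infer that the randomised comparison is absent. Section 12.4 does present results by arm as a general rule. What it lacks is an effectiveness estimand, with population, time point and interval.
- A reader might treat the 12 pairs as a multiple-testing failure. Twelve independent tests would give 1 − 0.95^12 = 0.46, and eight would give 0.34. But the plan states no alpha or decision rule for effectiveness and says that it will explore. Significance here is only a gauge of bias.
- A reader might blame the respiratory gate. It is met by any oxygen or nasal cannula, and Cohorts 1 and 2 reach target by Days 3 and 7. It adds little next to death and stopping.
- A reader might expect the two dose metrics to give significant results in opposite directions. That occurred in at most 4% of simulated trials. More often one is significant and the other is not.

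The separate SAP may set covariates and a hierarchy, and the model is multivariable. Adjusting for baseline severity would not cure step 4, because the bias there remains with no severity link at all.

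A randomised contrast is also imperfect here. The required echocardiogram is timed from the last dose (Section 4.4), and pooling cohorts averages over a four-fold range of target dose. These points shape the fix but do not remove the need for it.

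**Conclusion.** The concern holds in this form: the stated effectiveness analysis relates outcome to a post-randomisation dose, and no randomised effectiveness estimate is specified beside it. The main bias is total dose shortened by death or illness, which makes an inert drug look protective. The escalation gate is a smaller bias on maximum dose, toward apparent harm.

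At an assumed 5% mortality by Day 28 and a two-sided 0.05 level, total dose against 28-day death is nominally significant in roughly one third to two thirds of inert-drug trials without cohort stratification and in up to 99% with it. The randomised contrast stays at about 3% to 6%. The size depends on the death rate, the test used and whether placebo infants enter as dose 0. The direction follows from dosing ending at death.

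The documents do not support saying that the trial will make a false efficacy claim. The change should be made because the stated analysis can mislead and the remedy is cheap.

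**What to change.** In Section 12.4:

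1. Name one lead effectiveness estimate: sildenafil versus placebo in the ITT population, stratified by cohort, for centrally read PH combined with death, so that deaths before the echocardiogram are counted. Report a risk difference with a 95% confidence interval and make no significance claim. Show PH alone and death alone beside it.
2. Use the follow-up Day 1 (+2 days) echocardiogram, the only one required after baseline (Section 4.4, Table 6). State how three groups are handled: early stoppers, who are read sooner; weaned Cohort 2 and 3 infants, who are read about 6 days later than Cohort 1 completers; and infants randomised but never dosed, who have no such visit.
3. Label the maximum-dose, total-dose and PK/PD models supportive and non-causal. Do not relate total dose to death without accounting for dosing cut short by death or stopping.
4. If assigned target dose is modelled, compare it with cohort-matched placebo and state that cohorts are sequential, so target dose is not randomised between them.

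The cost is a few lines of text and one stratified analysis of data already collected. The price is candour about precision: about ±17 percentage points at an assumed 20% to 25% risk.

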exponential increase in sildenafil use by > 1000%, second highest of all drugs from 2005 to 2010.⁴⁴ Of the infants exposed to sildenafil, 79% had BPD and 84% had PH.

A phase 1 opportunistic pilot study of sildenafil in premature infants under IND (NCT01670136) has been completed. Conducted under IND by the PTN, the trial enrolled 34 infants ≤ 28 weeks gestational age with a median birth weight of 666 g receiving intravenous (IV) or enteral sildenafil per standard of care at doses between 0.13 mg/kg - 2.1 mg/kg. Pharmacokinetic and safety analyses were performed and are summarized below.

The infant population PK model identified safe sildenafil starting doses for early phase trials. Using 109 plasma samples collected in 34 infants in a multicenter phase 1 open-label PK study of sildenafil in premature infants, we developed a 2-compartment population PK model of sildenafil and its primary active metabolite N-desmethylsildenafil (DMS). Population estimates of parent sildenafil elimination clearance and central volume of distribution were 27.8 L/h/70kg and 116 L/70kg; relative DMS elimination clearance and volume of distribution, were 135 L/h/70kg and 1670 L/70kg.² The model simulated sildenafil and DMS exposures at different enteral and IV dosing regimens to identify safe doses for evaluation in a dose escalation trial (Table 1). Starting doses of 0.5 mg/kg IV (or 1 mg/kg enteral) resulted in combined AUC_{0-24,SIL+DMS} comparable to a previously reported value of 2650 ng*hr/mL which has been associated with infant survival.⁴⁵ However, exposure targets for PH prevention in infants with severe BPD are unknown and will be further elucidated in this trial.

Table 1 Simulated Median Steady-State Area under the Concentration vs. Time Profile 0- 24 Hours

Intravenous Dosing (every 8 hours)	0.5 mg/kg	1 mg/kg
Sildenafil (ng*hr/ml)	3157	6314
DMS (ng*hr/ml)	669	1337
Sildenafil + 62.5%DMS (ng*hr/ml)	3581	7163
Enteral Dosing (every 8 hours)	1 mg/kg	2 mg/kg
Sildenafil (ng*hr/ml)	1825	3650
DMS (ng*hr/ml)	1608	3217
Sildenafil + 62.5%DMS (ng*hr/ml)	2941	5883

Abbreviation: DMS, N-desmethylsildenafil

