5.4 Treatment Assignment Procedures

5.4.1 Randomization Procedures

Randomization will occur on Day -1 among participants who satisfy all eligibility criteria. Participants will be centrally randomized via the EDC to maintain a 3:1 ratio within each cohort of sildenafil (n=30) to placebo (n=10). Participants from a multiple gestation will be randomized independently as they become eligible. If more than one infant from a multiple gestation is randomized, the sibling relationship between participants will be collected in the eCRF.

Reasons for premature discontinuation will be noted on the electronic case report form (eCRF). A randomized participant who prematurely discontinues from the study prior to receiving 7 days of study drug may be replaced with a new participant who will receive the same randomization assignment. Replacement will not be allowed if the reason for premature discontinuation is related to study drug (Safety Medical Monitor deems the event relationship as Possible, Probable, or Definite). The randomization process will not determine if an IV or enteral dose is used. Route of administration, IV or enteral, will

be left to investigator discretion. Participants should not have an IV placed specifically for study drug administration alone. However, if an investigator deems that a second IV would optimize the safe administration of other medications or fluids while the participant is receiving the study drug, then an additional IV is permissible. If the participant does not have an IV or if the clinical team elects to use enteral dosing, then the dose of study drug will be twice that of the IV dosing (from the product label). Infants may transition from enteral to IV sildenafil (and vice versa) throughout the duration of the study per the investigator's determination. Placebo will be administered either enterally or IV in the same manner.

Study randomization codes and replacement codes for all cohorts will be generated and uploaded prior to the enrollment of the first participant. One sequential dosing cohort will be available at a time for assignment. Subsequent cohort slots will only become available after completion of safety reviews. Unblinded results will only be shared with blinded members of the study team following database lock. Any unplanned unblinding of individual or treatment group-level data will be reported to the study PI. Unplanned unblinding will be reported to NHLBI Program Officer and the DSMB.

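### The preliminary-effectiveness model uses unconverted sildenafil dose, although the enteral dose is by rule twice the IV dose and route is not randomized

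*Combined protocol and SAP*

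**What the plan says.** Section 12.4 (Preliminary Effectiveness) plans a multivariable mixed-effects model for the "relationship between the maximum and total dose of sildenafil and change in PH, death, and death or PH". Outcomes are taken at 28 days of study drug and again at the end of hospitalization or 52 weeks PMA, whichever is first. The text gives no unit for dose, lists no covariates and mentions neither a route term nor a conversion.

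Under Section 5.4.1, randomization does not set the route. If there is no IV, or the clinical team prefers enteral dosing, "then the dose of study drug will be twice that of the IV dosing (from the product label". Route can also change: "Infants may transition from enteral to IV sildenafil (and vice versa) throughout the duration of the study". Tables 3 and 4 carry the 2:1 ratio through every cohort and escalation step. Section 5.4.1 discourages placing a line only for study drug, and the footnote to the dosing table in the Protocol Summary favors IV when the infant already has a usable line.

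Section 2.2 treats the two routes as a pair at that ratio: "Starting doses of 0.5 mg/kg IV (or 1 mg/kg enteral) resulted in combined" AUC comparable to a published value. The Table 1 medians for IV 0.5 and 1 mg/kg are "Sildenafil (ng*hr/ml) 3157 6314" and "DMS (ng*hr/ml) 669 1337". For enteral 1 and 2 mg/kg they are "Sildenafil (ng*hr/ml) 1825 3650" and "DMS (ng*hr/ml) 1608 3217".

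Sections 3.2.2.1 and 3.2.2.2 separately plan individual exposure metrics from the population PK model and a PK/PD model for PH.

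**The concern.** A milligram given enterally and a milligram given IV are not the same exposure, and the protocol doubles the enteral dose for that reason. A model that enters dose as given undoes the correction: it credits enteral infants with twice the dose for an exposure that Table 1 puts somewhat lower.

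Route is also not random. It depends on whether a line is present or needed for other care, which plausibly follows how ill the infant is. If IV infants have more PH or death for that reason, low nominal dose goes with bad outcome and an inert drug can look protective. If IV infants do better, the bias runs the other way. If the drug works, a misordered dose variable blurs its effect. What is at stake is the dose-response reading that would inform a later efficacy trial, not the primary hypotension endpoint.

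**Working it through.** **Inputs.** Table 1 (simulated median steady-state AUC over 24 hours, ng*hr/mL), Table 4 (escalation schedule, every 8 hours, so 6 doses per 2-day step and 84 doses in 28 days), Table 5 (wean). Assumptions: dose in mg/kg, one route throughout, full schedule, and exposure proportional to dose beyond Table 1.

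**1. Check of Table 1.** Combined AUC = parent + 0.625 × DMS.
- IV 0.5 mg/kg: 3157 + 0.625 × 669 = 3575 (stated 3581).
- IV 1 mg/kg: 6314 + 0.625 × 1337 = 7150 (stated 7163).
- Enteral 1 mg/kg: 1825 + 0.625 × 1608 = 2830 (stated 2941).
- Enteral 2 mg/kg: 3650 + 0.625 × 3217 = 5661 (stated 5883).

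The gaps (0.2% IV, 3.8% enteral) are not an error, because the median of a sum need not equal the sum of medians. The stated values are used below.

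**2. Same cohort (enteral mg/kg = 2 × IV mg/kg), IV/enteral exposure.**
- Combined: 3581/2941 = 1.22, and 7163/5883 = 1.22 (1.26 if recomputed from the parts).
- Parent: 3157/1825 = 1.73.
- DMS: 669/1608 = 0.42.

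**3. Equal maximum dose.** Cohort 1 enteral and Cohort 2 IV both reach 1 mg/kg. Combined: 7163/2941 = 2.44. Parent: 6314/1825 = 3.46. Cohort 2 enteral and Cohort 3 IV tie in the same way at 2 mg/kg.

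**4. Total dose (mg/kg).** IV over 28 days:
- Cohort 1: 6 × 0.25 + 78 × 0.5 = 40.5.
- Cohort 2: 6 × (0.25 + 0.5 + 0.75) + 66 × 1 = 75.
- Cohort 3: 6 × (0.25 + 0.5 + 0.75 + 1 + 1.5 + 1.75) + 48 × 2 = 130.5.

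The wean adds 6 × (0.75 + 0.50 + 0.25) = 9 times the last dose in Cohorts 2 and 3. Enteral totals are double.

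| Cohort | IV, 28 days | Enteral, 28 days | IV with wean | Enteral with wean |
|---|---|---|---|---|
| 1 | 40.5 | 81 | 40.5 | 81 |
| 2 | 75 | 150 | 84 | 168 |
| 3 | 130.5 | 261 | 148.5 | 297 |

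Cumulative combined exposure, IV over enteral:
- Cohort 3 IV against Cohort 2 enteral: (130.5 × 7163)/(150 × 2941) = 2.12. With wean: (148.5 × 7163)/(168 × 2941) = 2.15. Enteral ranks higher on dose both times.
- Cohort 2 IV against Cohort 1 enteral: (75 × 7163)/(81 × 2941) = 2.26, with enteral ranked higher (81 against 75). With the wean, IV ranks higher (84 against 81) and the reversal is gone.

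**5. Illustration of bias.** Logistic simulation with an inert drug, 90 sildenafil infants and 28-day total dose. The documents give no route shares or route-specific risks, so these are assumed. A false protective signal is p<0.05 in the protective direction (nominal 2.5%). Ranges cover repeated runs.

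| IV share | Risk IV / enteral | False signal, nominal dose |
|---|---|---|
| 50% | 30% / 15% | 11% to 13% |
| 50%, with 30 placebo infants at zero dose | 30% / 15% | 8% |
| 20% | 30% / 15% | 7% to 8% |
| 50% | 25% / 20% | 3% |
| 50% | 35% / 10% | 31% to 33% |

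In the first row the median odds ratio is about 0.6 per 130.5 mg/kg (0.76 with placebo infants). IV-equivalent dose gives about 1.0, with 2% to 3% false signals. Keeping nominal dose but adding route gives 1.02 and 1.4%.

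**The case against.** - **An exposure analysis is already planned.** The PK/PD model in Section 3.2.2.2 uses model-based exposure, and Section 12.1 ties preliminary effectiveness to PK/PD. This stands for PH. It does not extend to death or death-or-PH, which the Section 12.4 model also covers. Results by arm and dose cohort are not affected by the route problem.
- **Route may yet be handled.** The model is multivariable with no covariates listed, and Section 12.4 defers detail to a separate analysis plan that is not among the documents. Adjustment is unstated, not excluded, and a route term alone removes most of the false signal in the simulation. Even so, the text names the exposure variable, and the variable named is unconverted.
- **The false-signal rates rest on assumptions.** This stands. They run from near nominal to about a third, and the direction reverses if IV infants fare better. The simulation also fixes route and is simpler than the planned model.
- **The metabolite runs the other way.** On DMS alone the enteral infant has more exposure, so mg/kg orders same-cohort infants correctly. The misordering concerns parent drug and the combined measure, which is the one Section 2.2 uses as its yardstick.

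A reader might also infer that the 2:1 rule ranks enteral infants above same-cohort IV infants with more than twice their exposure. Table 1 does not support that: the same-cohort ratios are 1.22 and 1.73. The 2.44 arises where the two infants tie on maximum dose.

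**Conclusion.** The concern holds for this one model. Used as written, maximum and total dose order same-cohort infants against their simulated exposure (1.22-fold combined, 1.73-fold parent). They tie infants whose combined AUC differs 2.44-fold. On total dose they place Cohort 2 enteral above Cohort 3 IV, which has about 2.1 times its cumulative exposure, with or without weaning doses. The Cohort 1 enteral over Cohort 2 IV reversal applies only to totals that leave out the wean.

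Dose therefore carries route, and plausibly illness, into the dose-response. It would go too far to say that the preliminary effectiveness answer is unreliable whatever happens: the bias cannot be sized from the documents, and PH has a second, exposure-based analysis. The conclusion rests on reading dose as mg/kg (plain mg would keep the doubling and add body weight), on dose proportionality, and on the separate analysis plan not already converting for route. As the model is exploratory and secondary in a safety trial, this is a cheap improvement.

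**What to change.** In Section 12.4, or in the separate analysis plan:

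1. Replace maximum and total dose with IV-equivalent maximum and total mg/kg, dividing each enteral dose by the protocol's own factor of 2. This handles route switches dose by dose.
2. State whether weaning doses count at each of the two time points.
3. Add first-dose route as a covariate.
4. Use individual AUC from the population PK model as a supporting analysis, with a stated rule for infants without PK samples. Section 8.2.2.1 samples only after 7 days at the target dose, so infants who die or stop early may have none. AUC is therefore the weaker main variable for death outcomes.

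The cost is one derived variable and one more fitted covariate. Section 4.2 already collects date, time, amount and route of dosing, and Section 4.3 does so during the wean. The factor of 2 is approximate: enteral combined AUC is 2941/3581 = 82% of IV at the doubled dose. Infants tied on IV-equivalent dose still differ 1.22-fold, against 2.44-fold when tied on nominal dose. No dosing or trial conduct changes.
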